8.2.2 Subject Exclusion Criteria

Subjects meeting any of the following criteria will be excluded from the study:

E01 Phenylketonuria

E02 Acute or chronic medical conditions, organ system disease, or medications that, in the principal investigator's opinion, would impair the subject's ability to participate

E03 TMD

- E04 Self-reported allergy to sucralose or mint flavors
- E05 Self-reported use of tobacco products including e-cigarettes
- E06 Use of any type of anticoagulant medications (eg clopidogrel)
- E07 Routine use of proton pump inhibitors
- E08 Allergic to any component of the study drug
- E09 Gross oral pathology, including widespread caries or chronic neglect, extensive restoration, pre-existing gross plaque or calculus, or soft or hard tissue tumor of the oral cavity
- E010 Orthodontic appliances or removable partial dentures that will compromise the ability of the potential subject to participate in the study
- E011 Periodontitis as indicated by periodontal pockets greater than 4 millimeters on more than one site
- E012 Receipt of any investigational drug/test product within 30 days prior to study entry with study entry defined as Day 0, or currently participating in either the active or follow-up phase of any other investigational study or planning to participate in any other investigational study during participation in this trial
- E013 Participation in the Phase 1/2a antiplaque study
- E014 Receipt of antibiotics within 30 days prior to study entry
- E015 Need for antibiotic prophylaxis prior to invasive dental procedures
- E016 Receipt of prescription antibacterial oral products (eg products containing chlorhexidine) within 30 days prior to study entry
- E017 Pregnant or breast-feeding female
- E018 An employee of the study site directly involved with the study
- E019 Inability to comply with assigned treatment regimen

8.3 Subject Withdrawal Criteria

A subject may withdraw consent at any time during the study without penalty. The PI may discontinue the subject's activity without the subject's consent if any of these criteria is met:

- A subject fails to comply with study procedures
- A subject's safety or health may be compromised by further participation

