8.3.1 When and How to Withdraw Subjects

A subject may end his or her participation in the study at any time. If a subject withdraws, the Principal Investigator will make a reasonable effort to determine the reason for the withdrawal from the study and to complete termination procedures as described in [section 8.5.2](#) and [section 8.5.4](#). Telephone calls, registered letters, and email correspondence are considered reasonable

effort. For subjects leaving the study, a targeted examination may be performed, if medically indicated and if permitted by the subject.

A subject may be withdrawn for an AE or SAE resulting in a safety concern. When a subject withdraws due to an AE or is withdrawn by the principal investigator due to an AE, the sponsor's safety office, the USAMRMC Clinical Services Support Division (CSSD), Product Safety Surveillance Branch (PSSB), must be notified within 72 hours ([contact]). The Principal Investigator must follow specific policy regarding the timely reporting of AEs and SAEs to the US Investigational IRB as the IRB of record ([section 11.5.1.2](#)). In all cases, the Principal Investigator will make a reasonable effort to complete study termination procedures.

If a subject meets withdrawal conditions for a concomitant medication violation or noncompliance, this should clearly be stated in the source document and the study termination eCRF.

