12.8 Selection of Subjects to be Included in Analyses

The Full Analysis Set (FAS) is defined as all randomized subjects having Baseline and Day 4 QHT evaluations, with the Day 4 evaluation occurring on the morning following the last chewing gum treatment from the previous day. The FAS population will be analyzed according to their randomized treatment assignment.

The Per Protocol Population (PP) is a subset of FAS and consists of all subjects with no major protocol violations such as: failure to obtain valid informed consent, accidental distribution of incorrect study medication, not following the inclusion/exclusion criteria, evidence that study medication was not taken, and the performance of oral hygiene other than chewing the study gum during the study period. Analysis of the PP will be according to the treatment actually received by the subject.

The Safety Population consists of all randomized subjects receiving at least one dose of study medication, and summarized on the basis of treatment received. All AE summaries will be based on the safety population.

13 Direct Access to Source Data/Documents

Subjects will be identified on eCRFs by a unique subject identification number and on source documents by name and date of birth. No personal identifier will be used in any publication or communication used to support this research study. The subject identification number will be used if it becomes necessary to identify data specific to a single subject. Representatives of USAMRMC, the sponsor's representative, the IRB of Record and/or the USAMRMC ORP, and the FDA are eligible to review medical and research records related to this study as a part of their responsibility to protect human subjects in clinical research. Personal identifiers will be removed from photocopied medical and research records.

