6.1. Data Handling Conventions

6.1.1. Study Analysis Populations

The Safety Population consists of all subjects receiving at least one dose of study medication. These will most likely be randomized subjects receiving study therapy at Visit 3 (Day 0). The safety population will be analyzed according to the treatment actually received (KSL-W or placebo).

The Full Analysis Set (FAS) is defined as all randomized subjects having Baseline and Day 4 QHT evaluations, with the Day 4 evaluation occurring on the morning following the last chewing gum treatment from the previous day. The FAS population will be analyzed according to their randomized treatment assignment. A randomized subject with a missing Day 4 QHT whole mouth score will not have this score imputed, and will not be in the FAS cohort.

The Per Protocol Population (PP) is a subset of FAS and consists of all subjects with no major protocol violations itemized as follows: failure to obtain valid informed consent, accidental distribution of incorrect study medication, not following the inclusion/exclusion criteria, evidence that study medication was not taken, and the performance of oral hygiene other than chewing the study gum was during the study period, Day 4 evaluation performed later than on the morning following the last chewing gum treatment from the previous day. Analysis of the PP will be according to the treatment actually received by the subject.

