7.4.4. Major Protocol Violations

Major protocol violations will be listed by subject as well as summarized by study arm for the FAS population.

8. Data Receipt and Analysis Plan Modification

Refinements to this analysis plan were made during the course of the study. The changes from the original analysis plan are incorporated in this final analysis plan, which was completed and approved by the study sponsor and ClinSmart before database lock and unblinding. Any deviations to the SAP will be explained in the SAR and final CSR.

9. Interim Analysis, DSMB

No interim analysis will be performed, and no data safety monitoring board will be used for this study.

10. Display and Formatting of Tables and Listings

All tables and listings will be produced in Rich Text Format, landscape mode. A separate copy of the tables and listings will be produced in an Adobe format.

A reference to appropriate subject listings will be provided below each table.

Rounding Conventions

- All computations will be generated using data with full decimal expansion, and rounding will occur only for the outputted summaries.
- All summarized QHT scores will be rounded to the nearest hundredth, and a 5 in the hundredth's place will always be rounded to 6. For example, the score 3.285 will be rounded to 3.29.
- Adverse event rates (number of events/total exposure) will be rounded to the nearest hundredth.
- All other summary percentages will be rounded to the nearest tenth: $100*(3/9) = 33.3333$ will be recorded as 33.3%.

11. Table Shells

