11.2. Table Shells

TREF01

Subject Disposition

	Total	KSL-W	Placebo
Number Screened	xx		
Number Randomized	xx	xx	
Number Receiving Study Drug	xx	xx	
End of Study Status			
Number (%)* Completing Study	xx (%)	xx (%)	xx (%)
Number (%) with Early Discontinuation	xx (%)	xx (%)	xx (%)
Reason for Early Discontinuation			
Screening failure			
Adverse Event			
Lost to Follow-up			
Terminated by Principal Investigator			
Major Protocol Deviation/Deviation			
Subject requested to be withdrawn			
Sponsor decision to withdrawal	xx		xx

*(%) = percentage of those randomized, within total and each study arm

Subject Listing: LREF01, LREF12, LREF21b, LREF13

TREF02				
Analysis Populations				
		Total	KSL-W	Placebo
Number in Safety Population*		xx	xx (%)	xx (%)
Number in Full Analysis Set**		xx	xx (%)	xx (%)
Number in Per-Protocol Population***		xx	xx (%)	xx (%)

(%) = Percent of total

*Subjects receiving at least one dose of study therapy, analyzed according to the therapy received

**Subjects having a valid QHT evaluation at Study Days 1 and 4, analyzed as randomized

***Subjects in the Full Analysis Set with no major protocol deviations (see table TREF15 for a summary of major protocol deviations)

Subject Listing LREF12, LREF21b, LREF18

number screened: ENROLLMENT.ICFDT pg 2 eCRF

number randomized: RAND.RANDYN pg 36 eCRF

number in Safety pop: DRUGADMIN.DISPSCYN pg 46 eCRF

Number in Per-Protocol Population: from protocol dev. pg 101 eCRF, and a list of subjects with no major protocol Deviations

TREF03.1

Demographic Assessments

Safety Population: KSL-W (N=xx), Placebo (N=xx)

	KSL-W	Placebo	Total
Age (years)			
mean (std. dev)	xx.x (x.x)
Minimum, Median, Maximum

Gender, n (%)			
male	xx (xx)
female
unknown (not given)
Ethnicity, n (%)			
Hispanic or Latino	Xx (XX) (%)
Not Hispanic or Latino
Not reported, Unknown

Race, n (%)			
White	
Native Hawaiian, Other Pacific Islander
Black or African American
Asian
Other

Percentages may not add up due to rounding

Subject listing: LREF01

(TREF03.2 FAS, TREF03.3 Per-Protocol Population)

From Enrollment, pg 2 eCRF

TREF04.1

Medical History, Urine Drug Screen

Safety Population: KSL-W (N=xx), Placebo (N=xx)

		KSL-W	Placebo	Total
Does the subject have any relevant medical history? (past/concomitant diseases or surgeries)				
Yes*		n (%)	n (%)	
No		n (%)	n (%)	
Not collected		n (%)	n (%)	

Was Urine Drug Screen Performed?

Yes		n (%)	n (%)	
	Result			
	positive	n (% of yes)	n (% of yes)	

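### Discontinuing a subject for non-compliance can cost the Day 4 plaque score and a place in the FAS, although the analysis sets treat non-compliance as a Per Protocol exclusion

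*Protocol*

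**What the plan says.** **Discontinuation.** Protocol 8.3 states: "The PI may discontinue the subject's activity without the subject's consent if any of these criteria is met". One of the two criteria is "A subject fails to comply with study procedures", with no threshold. Section 8.3.1 also refers to "withdrawal conditions for a concomitant medication violation or noncompliance". Among the reasons for early discontinuation, SAP table TREF01 lists termination by the investigator and "Major Protocol Deviation/Deviation".

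**Follow-up after discontinuation.** Protocol 8.3.1 adds: "In all cases, the Principal Investigator will make a reasonable effort to complete study termination procedures". Section 8.3.4 identifies these procedures as Visit 3, which the site will try to schedule. Visit 3 includes the QHT (Protocol 9.1.4). It is the Day 4 visit, numbered Visit 4 in the SAP.

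**Analysis sets.** In Protocol 12.8 and SAP 6.1.1 the FAS needs a baseline and a Day 4 QHT, with the Day 4 evaluation on the morning after a chew taken the day before. Under SAP 6.1.1, a randomized subject with no Day 4 score "will not have this score imputed, and will not be in the FAS cohort". The PP set is a subset of the FAS. Its exclusions include "evidence that study medication was not taken, and the performance of oral hygiene other than chewing the study gum during the study period". The SAP adds a late Day 4 evaluation to the PP violations.

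**Exposure and reporting.** SAP 6.1.2 credits Day 4 completers with full exposure whether or not they took any unsupervised gum. On violations, SAP 7.4.4 says: "Major protocol violations will be listed by subject as well as summarized by study arm for the FAS population".

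**The concern.** The analysis sets imply that a subject who skips gum or brushes stays in the as-randomized comparison and leaves only the PP set. The withdrawal rule gives another route: the same subject can be discontinued, miss the Day 4 score and drop out of both sets. Whether that happens depends on a discretionary decision made after randomization, about behaviour that may differ by arm.

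This matters because of how the QHT result will be used. Its p-values are descriptive, but the KSL-W minus placebo difference and the error SD are the main proof-of-concept summaries (Protocol 12.3) and feed the forecast for later studies (Protocol 12.1.2.1). With 13 subjects randomized per arm and no replacement (Protocol 5.7, 8.3.3), one or two exclusions can move the estimate.

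**Working it through.** **Step 1: how a non-compliant subject leaves the FAS.** There are two routes.

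- *Discontinued under 8.3.* Sections 8.3.1 and 8.3.4 promise an effort to hold Visit 3. They set no day and do not say that a QHT taken then counts as the Day 4 score. Section 8.3.2 commits only to reporting data up to withdrawal. The synopsis treats a Day 4 evaluation more than 24 hours late as loss to follow-up.
- *Not discontinued, but stopped chewing before Day 3.* The subject is scored on Day 4, but not on the morning after a chew the day before. Read literally, the FAS definition excludes this subject too, which conflicts with treating gum not taken as a PP matter.

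The SAP also names late Day 4 evaluation both in the FAS definition and as a PP violation. TREF18 is based on the FAS and has a row for late evaluation. Under the literal FAS definition that row must be empty.

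**Step 2: the plan's own figures.** The stated probabilities (at least 94% and at least 81% with 12 per arm) are not in dispute. The prior is not specified. A simulation from the phase 2a figures, with an assumed non-informative prior on 21 degrees of freedom, gives 97.5% and 91.7%, so the bounds are met.

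**Step 3: illustration of size.** Inputs from the documents:

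- benefit 0.31 − 0.03 = 0.28 and error SD 0.22 (Protocol 12.2, SAP 5.4)
- 13 per arm (Protocol 5.7)
- two-sided 0.05 and 90% power for the confirmatory study (Protocol 12.2)

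Assumption: k of 13 KSL-W subjects do not chew and respond like placebo. The documents give no rate, so k runs from 1 to 3.

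- Expected difference with everyone kept: d = 0.28 × (13 − k)/13. With the k subjects removed it is 0.28.
- Projected n per arm = 2 × (1.960 + 1.2816)² × 0.22² / d² = 1.017/d², rounded up.
- Standard error with 13 per arm: 0.22 × √(2/13) = 0.086.

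| k | d, all kept | d, removed | overstatement | n per arm, all kept | n per arm, removed |
|---|---|---|---|---|---|
| 1 | 0.258 | 0.28 | 0.022 | 15.2, so 16 | 13.0, so 13 |
| 2 | 0.237 | 0.28 | 0.043 | 18.1, so 19 | 13 |
| 3 | 0.215 | 0.28 | 0.065 | 21.9, so 22 | 13 |

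**Step 4: direction.** Suppose instead that 1 to 2 placebo subjects brush, and that brushing lowers their Day 4 score by 0.28 to 1.0 (assumed). The as-randomized difference is then between 0.28 − 0.28/13 = 0.258 and 0.28 − 2 × 1.0/13 = 0.126, so removing them overstates the effect. If one KSL-W subject brushes, with a drop of 0.28, the as-randomized difference is 0.28 + 0.28/13 = 0.302, and removal understates it.

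**The case against.** The strongest reply is that withdrawal does not in itself delete the Day 4 score. Discontinuation is optional, and the effort to complete termination procedures applies in all cases and leads to a visit that includes the QHT. No visit falls between Day 0 and Day 4, and used gum is returned on Day 4. Apart from the online diary, most non-compliance would surface at the visit where plaque is scored. Protocol 7.4.4 classes unreturned product and missed doses as deviations, and SAP 6.1.2 expects completers who took no unsupervised gum. All of this stands. A reader might infer that withdrawal always removes the subject from the FAS, or that a failed hygiene check ends the visit before scoring. The documents support neither: the loss is possible, not automatic, and the order of the Visit 3 list is not stated to be binding.

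A reader might also infer a bias in favour of KSL-W through taste change or coated tongue. Protocol 5.6.1.1 lists these as risks, but Protocol 5.5.2 reports dysgeusia and coated tongue at 50 and 75 mg over 28 days and does not list them for 4 to 30 mg. Differential non-adherence at 30 mg over four days is not shown. The investigator is blinded, which limits deliberate selection but would not remove a difference in adherence between arms.

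Nor do withdrawn violators vanish from the reports. TREF01 gives discontinuation reasons by arm, and LREF13 and LREF18 list withdrawals and deviations. Only the by-arm summary of violations misses those outside the FAS.

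What the reply does not answer is that the recovery effort has no fixed day and no stated use in the analysis, and that the FAS chew condition excludes early non-chewers even when every visit is completed.

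**Conclusion.** The point holds as an inconsistency that should be resolved. The withdrawal rule and the FAS chew condition can each remove non-compliant subjects from the as-randomized plaque comparison, contrary to the role the plan gives the PP set. The resulting bias can run either way and cannot be sized from the documents. Under the stated assumption about KSL-W non-chewers, one or two removals overstate the difference by 0.022 to 0.043, a quarter to a half of its standard error, and shrink the projected confirmatory size from 16 to 19 per arm to 13. Those figures are illustrative only. The QHT is a secondary endpoint with descriptive p-values, and the primary safety analysis does not use the FAS, so the consequence is confined to the proof-of-concept estimate and the forecast built on it.

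**What to change.** 1. Reconcile Protocol 8.3, 8.3.1 and 8.3.4 with Protocol 12.8 and SAP 6.1.1. State that non-compliance does not end study assessments: the subject still attends the Day 4 visit, has the QHT scored, is analysed in the FAS as randomized, and is excluded only from the PP set. Leave the safety ground, and any decision on stopping study product, as they are.
2. In Protocol 12.8 and SAP 6.1.1, take the previous-day chew condition out of the FAS definition and keep the chew and timing conditions in the PP definition only. Without this, change 1 does not retain subjects who stopped chewing before Day 3.
3. Base SAP 7.4.4 and TREF18 on all randomized subjects. This is a small gain, since TREF01, LREF13 and LREF18 already show withdrawals and deviations.

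The cost is a few lines in each document and one population label, with no extra visit or subject. The FAS estimate may become slightly smaller and noisier; the PP analysis remains available for the adherent subjects.

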8.3.1 When and How to Withdraw Subjects

A subject may end his or her participation in the study at any time. If a subject withdraws, the Principal Investigator will make a reasonable effort to determine the reason for the withdrawal from the study and to complete termination procedures as described in [section 8.5.2](#) and [section 8.5.4](#). Telephone calls, registered letters, and email correspondence are considered reasonable

effort. For subjects leaving the study, a targeted examination may be performed, if medically indicated and if permitted by the subject.

A subject may be withdrawn for an AE or SAE resulting in a safety concern. When a subject withdraws due to an AE or is withdrawn by the principal investigator due to an AE, the sponsor's safety office, the USAMRMC Clinical Services Support Division (CSSD), Product Safety Surveillance Branch (PSSB), must be notified within 72 hours ([contact]). The Principal Investigator must follow specific policy regarding the timely reporting of AEs and SAEs to the US Investigational IRB as the IRB of record ([section 11.5.1.2](#)). In all cases, the Principal Investigator will make a reasonable effort to complete study termination procedures.

If a subject meets withdrawal conditions for a concomitant medication violation or noncompliance, this should clearly be stated in the source document and the study termination eCRF.

8.3.2 Data Collected for Withdrawn Subjects

All data collected up to the time of withdrawal will be reported. The reason for withdrawal will be specified in the eCRF.

8.3.3 Replacement of Subjects

Subjects who withdraw from the study will not be replaced.

8.3.4 Follow-up for Withdrawn Subjects

Salus Research will attempt to contact any subject who withdraws from the study in an effort to determine the reason for withdrawal as well as to schedule a visit to conduct the study termination procedures (Visit 3). Reasonable effort will be made to complete final study documents.

9 Treatment of Subjects

9.1 Study Visits

9.1.1 Screening (Day -16 to -1) – Visit 1

Potential subjects will arrive at Salus Research and the informed consent process will proceed. After the informed consent document and the Authorization for the Release of Health Information (HIPAA) document are signed, the following procedures will occur:

- Inclusion and exclusion criteria will be evaluated
- A medical history with demographic information will be collected
- Vital signs (diastolic and systolic blood pressure, heart rate, respiration rate and temperature) will be collected
- A physical examination will be performed
- A urine drug screen will be performed
- Females of childbearing potential will take a urine pregnancy test
- A periodontal exam will be performed. This exam will include a determination of the number of teeth, scorable surfaces and pocket depths around teeth
- An intraoral examination (OST and OHT) will be performed
- Oral hygiene check - Subjects must have refrained from oral hygiene procedures (flossing, brushing of teeth, mouth wash rinse) for 12 to 16 hours prior to the screening visit.
- Supragingival plaque will be assessed using the QHT. (A red food dye will be used to disclose plaque deposits.)
- Concomitant medications will be recorded

A subject is not considered enrolled in the study until it is determined that he or she satisfies all of the inclusion and exclusion criteria ([section 8.3](#) and [section 8.4](#)).

9.1.2 Supervised Treatment, Study Day 0 (Baseline) – Visit 2

After the screening period, those subjects who are eligible for participation will return to the clinic for Visit 2 (Day 0 baseline). The following procedures will occur:

- The inclusion and exclusion criteria will be re-checked
- Vital signs (systolic and diastolic blood pressures, heart rate, respiration rate and temperature) will be measured
- Intraoral exam (OST and OHT) will be conducted
- Oral hygiene check: The subject will be asked to confirm that he/she did not perform any oral hygiene procedures (flossing, brushing of teeth, mouth wash rinse) for 12 to 16 hours prior to Day 0.
- Randomization (1:1)
- Supragingival plaque will be assessed using the QHT. (A red food dye will be used to disclose plaque deposits.)

- Licensed dental hygienist will polish teeth.
- The first chew will be administered under supervision in the clinic. The subject will be instructed to chew one tablet of gum for 20 minutes. Chewing should be balanced as equally as possible between both sides of the mouth.
- After chewing the gum for the designated time, the subject will be given a used product bag to store the chewed gum. The evaluator will inform the subject to label this bag with the time and date of the chew.
- After the chewing gum is stored in the used product bag, the subject will complete the start and stop times for chewing gum on the electronic diary information system (ePRO). The subject will enter this information while in the clinic.
- The study drug will be dispensed for unsupervised use. The subject will receive:
 - 13 gum tablets for their unsupervised use along with 13 individual used product collection bags.
 - Subjects will be given instructions for chewing the gum.
 - a. The gum will be chewed for 20 minutes preferably after a meal or every 4 to 6 hours (3 times a day). Chewing will be balanced as equally as possible between both sides of the mouth for a maximum of 3 chews per day.
 - b. After completing each 20 minute chew, subjects will store the used gum in the used product collection bags provided to them.
 - c. Subjects will label each used product collection bag with the date and time of chew. (A separate bag will be used for each chew).
 - d. After each chew, subjects will record the start and stop time of the chew on the electronic diary information system - ePRO (Instructions provided in [Appendix D](#))
 - e. Subjects will be informed that they must bring all of the used product collection bags back to the clinic for Visit 3
- Subjects will be told that no oral hygiene procedures of any kind (teeth brushing, flossing or mouth wash rinse) will be allowed while on study treatment (Day 0, 1, 2, 3 and 4).
- AEs from first chew will be collected.
- Concomitant medication will be recorded.

9.1.3 Unsupervised Treatment, Study Days 0, 1, 2, and 3

After the first supervised chew is completed, the subjects will be released from the clinic. There will be a total of 11 unsupervised, self-administered chews. The subjects will chew one tablet of the gum (study drug) for 20 minutes every 4 to 6 hours, preferably after a meal, for a maximum of 3 chews per day according to the schedule in [Table 6](#).

Table 6: Schedule for Unsupervised Chews:

Time ^a	Day 0	Day 1	Day 2	Day 3
After Breakfast ^b	N/A	1	1	1
After Lunch	1	1	1	1
After Dinner	1	1	1	1
Total Chews per Day	2	3	3	3

^a Gum will be chewed for 20 minutes preferably after a meal or every 4 to 6 hours for a maximum of 3 chews per day. Chewing will be balanced as equally as possible between both sides of the mouth.

^b First chew takes place in the clinic.

After completing each 20 minute chew, the subject will store the used gum in the used product collection bags provided to them. The subject will record the date and time of chew on the individual collection bags as instructed. A separate bag will be used for each chew. Subjects will record their chewing gum start and stop times on the electronic diary system (ePRO) after each chew.

9.1.4 Treatment, Study Day 4 – Visit 3

After 4 days of treatment, subjects will return to the clinic for Visit 3. The following procedures will occur at Visit 3:

- Subjects will return all used product bags and any unused product. Site Staff will collect used/unused product bags.
- Vital signs (diastolic and systolic blood pressures, heart rate, respiration rate and temperature) will be measured.
- A brief, symptom-oriented physical examination will be performed
- Females of child-bearing potential will take a urine pregnancy test
- Subjects will be asked to verify that he/she has refrained from all oral hygiene procedures (teeth brushing, flossing or mouth wash rinse) since their last chew.
- An intraoral exam (OST and OHT) will be performed.
- Supragingival plaque will be assessed using the QHT. (A red, food dye will be used to disclose plaque deposits on the teeth).
- AEs will be assessed.
- Concomitant medications will be recorded.

- Subject will be discharged from the study. (Subject will be allowed to brush their teeth just prior to leaving the research center is discharged from the study.)

